3.2 STUDY DRUG ADMINISTRATION

ZD6474 Administration

Treatment will be self-administered by the patient on an outpatient basis. The starting dose of ZD6474 is 300mg/day administered PO daily. Patients with moderate renal failure defined as creatinine clearance > than or = 30ml/min and <50ml/min should begin vandetanib at a reduced dose of 200mg. ZD6474 should be taken with some food and water to minimize GI effects, ideally at around the same time every morning. ZD6474 is available as 50mg, 100mg, 200mg and 300mg tablets and as an oral solution (15 mL of 10mg/mL vandetanib in 25 mg oral solution bottles). Patient compliance will be tracked using a pill count/administration form which the patient will be instructed to complete and which will be reviewed at each clinic visit. If the subject inadvertently does not take the dose in the morning, he or she may take that day's dose any time up to 10pm that same day. However, if a subject misses taking their scheduled dose and is unable to take the missed dose on the same day, he or she must take the next scheduled dose and the missed dose will not be made up.

Reported adverse events and potential risks are described in Section 8. Appropriate dose modifications for ZD6474 are described in Section 3.3. No investigational or commercial agents or therapies other than those described below may be administered with the intent to treat the patient's malignancy.

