2 ELIGIBILITY ASSESSMENT AND ENROLLMENT

2.1 ELIGIBILITY CRITERIA

2.1.1 Inclusion Criteria

- Patients must satisfy all the following criteria to be eligible for study enrolment

- Clinical diagnosis of von Hippel Lindau disease ([Appendix E](#))
- The presence of at least one measurable (as defined by RECIST) renal tumor (RCC). Patients with tumors localized to the kidney as well as those with metastatic RCC are eligible.
- Age \geq 18 years.
- Life expectancy $>$ 3 months
- Performance status ECOG 0-2
- Patients must have normal organ and marrow function as defined below: WBC count \geq 3,000/uL, absolute neutrophil count \geq 1,500/ \square , platelet count \geq 100,000/ \square , serum creatinine \leq 1.5 times upper limit of reference range or measured 24 hr. creatinine clearance \geq 50 ml/min, AST and ALT $<$ 2.5 x upper limit of reference range, total bilirubin $<$ 1.5x upper limit of reference range ($<$ 3 x upper limit of reference range in patients with Gilbert's disease), alkaline phosphatase \leq 2.5 x upper limit of reference range (or \leq 5 x upper limit of reference range if considered to be related to liver metastases by the PI)
- No history of serious intercurrent medical illness
- At least four weeks from completion of any other surgical or investigational therapy for von Hippel Lindau and at least 4 weeks from any major surgical procedure. In addition, patients who have undergone recent major surgery should have well healed surgical incisions.
- All men and women of childbearing potential must use effective contraception
- Negative pregnancy test in female patients of childbearing potential within 7 days prior to enrolment on study
- Ability to understand and the willingness to sign a written informed consent document.

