- QTc with Bazett's correction that is unmeasurable, or ≥ 480 msec on screening ECG. If a patient has QTc ≥ 480 msec on screening ECG, the screen ECG may be repeated twice (at least 24 hours apart). The average QTc from the three screening ECGs must be < 480 msec in order for the patient to be eligible for the study). Patients who are receiving a drug that has a risk of QTc prolongation (see [Appendix C](#), Group/Table 2) are excluded if QTc is ≥ 460 msec.
- Potassium concentration less than 4.0 mEq/L, calcium (ionized calcium or adjusted for albumin), or magnesium concentrations outside normal limits despite optimal supplementation/correction
- Left ventricular ejection fraction less than 45% measured by multiple gated acquisition scan (MUGA) or echocardiogram (ECHO)
- Hypertension not controlled by medical therapy (systolic blood pressure greater than 150 mmHg or diastolic blood pressure greater than 100 mmHg).
- Uncontrolled intercurrent illness including, but not limited to, ongoing or active infection, symptomatic congestive heart failure, unstable angina pectoris, cardiac arrhythmia, or psychiatric illness/social situations that would limit compliance with study requirements.
- Patient known to be HIV positive and requiring antiretroviral therapy
- Currently active diarrhea that may affect the ability of the patient to absorb ZD6474 or tolerate further diarrhea.
- Patients on therapeutic anticoagulation
- Patients with known bleeding disorders
- Pregnant women are excluded from this study because ZD6474 is an anti-angiogenic agent with the potential for teratogenic or abortifacient effects. Because there is an unknown but potential risk for adverse events in nursing infants secondary to treatment of the mother with ZD6474, breastfeeding should be discontinued if the mother is treated with ZD6474
- Any known hypersensitivity to ZD 6474 or other excipients of ZD6474

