2.2.3 The following must be performed within 7 days of enrollment on study

History and physical - Limited interim evaluation focusing on significant changes or deviations from initial H&P

CBC with differential, Chem 20 panel, urinalysis

Urine or serum pregnancy test in women of childbearing potential.

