3.5 STUDY EVALUATIONS AND SCHEDULE

3.5.1 Baseline Evaluation

These studies are intended to evaluate the presence and extent of nonrenal VHL-associated tumors and are not meant to determine eligibility. These studies may be performed before (as part of routine evaluation of VHL patients) or after eligibility assessment but no more than 3 months prior to study enrolment.

3.5.1.1 MRI of the spine to include: precontrast T-2 weighted surface coil images of the cervical and thoracic cord in the sagittal plane and post contrast (Gadolinium). CT imaging with and without contrast may be performed if MRI cannot be performed.

3.5.1.2 24 hour urine collection for catecholamine analysis when clinically indicated.

3.5.1.3 Standard complete audiogram to detect hearing loss and /or the presence of an ELST (endolymphatic sac tumor) in patients known or suspected to have these tumors.

3.5.1.4 CT examination of the internal auditory canal to evaluate for potential ELST in patients known or suspected to have these tumors.

3.5.1.5 For males, ultrasound of testicles with high resolution (5-7 MHz) transducer to evaluate the epididymis (0.75 hour scan time) when clinically indicated.

3.5.1.6 An ophthalmologic exam to screen for retinal angiomas.

3.5.1.7 Labs: serum erythropoietin, TSH, T3 and FreeT4, parathyroid function tests –spot urine phosphorous and spot urine creatinine, vitamin D 1-25, vitamin D 25-OH Serum PTH, FGF23 (1-2ml of plasma to be sent to [name]., Chief, Skeletal Clinical Studies Unit, CSDB, NIDCR)

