10.7 DOSAGE AND ADMINISTRATION

300mg/day administered orally. The drug should be taken with food and water to minimize GI effects. The tablets should not be taken with grapefruit juice. Tablets should not be crushed, chewed or otherwise divided and must be swallowed whole. Dose modifications will follow the scheme outlined in section 3.3.

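### The 200 mg starting dose depends on a creatinine clearance that no screening step obtains and section 3.2 does not define, and no dose or exclusion is stated below 30 ml/min.

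*Combined protocol and SAP*

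**What the plan says.** Section 3.2 gives the general rule, "The starting dose of ZD6474 is 300mg/day administered PO daily", and one renal exception: at clearance of at least 30 and below 50 ml/min, patients "should begin vandetanib at a reduced dose of 200mg". It states nothing for clearance below 30. Section 10.7 gives "300mg/day administered orally" with no renal exception. The lower dose levels in section 3.3 are triggered by toxicity, not by renal function.

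The renal part of the inclusion criteria (section 2.1.1) offers two alternatives joined by an or: serum creatinine at most 1.5 "times upper limit of reference range or measured 24 hr. creatinine clearance" of at least 50 ml/min. Section 2.1.2 contains no exclusion based on clearance.

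The laboratory work within 7 days of enrolment (section 2.2.3) is "CBC with differential, Chem 20 panel, urinalysis", plus a pregnancy test where relevant. The baseline laboratory list (section 3.5.1.7) includes "spot urine phosphorous and spot urine creatinine". The only 24-hour urine collection in the schedule is for catecholamines, when clinically indicated (section 3.5.1.2). Sections 2.2.2 and 3.5.2 and the calendar (section 3.6) list no clearance.

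**The concern.** A patient who qualifies by measured clearance has at least 50 ml/min and starts at 300 mg. The 200 mg rule can therefore matter only for patients admitted on serum creatinine, and that is the group for whom no clearance is required. The protocol judges that 30 to below 50 ml/min calls for a lower start, but does not schedule the value that triggers it. It also leaves open whether a measured or an estimated value counts.

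Below 30 ml/min, serum-route patients meet no numeric floor, and the only dose statement that covers them is the general 300 mg.

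What is at stake is initial exposure to a drug for which section 1.2.5 reports a concentration relation for QTc prolongation, a half-life of about 4-5 days, and marked accumulation to steady state by day 29. Reduced renal function is foreseeable in patients who often need repeated kidney surgery (section 1.2.6), although the documents give no renal-function distribution.

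**Working it through.** No stated figure is in dispute, so there is none to reproduce. The check is whether the two clearance bands can be reached within the eligibility limit.

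**Inputs from the plan.** Creatinine limit 1.5 x ULN (2.1.1); dose bands (3.2).

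**Assumptions, not in the plan.** ULN 1.0, 1.1 or 1.3 mg/dL, so the ceiling is 1.5, 1.65 or 1.95 mg/dL. Clearance is estimated by Cockcroft-Gault: (140 - age) x weight / (72 x creatinine), times 0.85 for women. Ages are 30 to 70 in steps of 10; women 50 to 90 kg and men 60 to 100 kg in steps of 10. This gives 25 profiles per sex.

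**Step 1. Profile counts out of 25, shown as 30 to <50 / below 30.**

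| ULN (mg/dL) | Women, at 1.5 x ULN | Men, at 1.5 x ULN | Women, at ULN | Men, at ULN |
|---|---|---|---|---|
| 1.0 | 13 / 1 | 3 / 0 | 3 / 0 | 0 / 0 |
| 1.1 | 14 / 2 | 6 / 0 | 4 / 0 | 0 / 0 |
| 1.3 | 16 / 6 | 12 / 1 | 9 / 0 | 1 / 0 |

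The first pair of columns is the worst case, with every profile at the ceiling. The second pair sets creatinine at the ULN. These are counts of profiles, not proportions of patients.

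**Step 2. Who falls below 30 at the ceiling.**
- ULN 1.0: woman, 70 y, 50 kg: 70 x 50 x 0.85 / (72 x 1.5) = 27.5 ml/min.
- ULN 1.1: the same woman, 25.0; woman, 60 y, 50 kg: 80 x 50 x 0.85 / (72 x 1.65) = 28.6.
- ULN 1.3: six women (50 kg at 50, 60 and 70 y; 60 kg at 60 and 70 y; 70 kg at 70 y) and one man (70 y, 60 kg, 29.9).

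**Step 3. Creatinine at which clearance reaches 50.**
- Woman, 60 y, 60 kg: 80 x 60 x 0.85 / (72 x 50) = 1.13 mg/dL. She reaches 30 only at 1.89 mg/dL, which is inside the limit only if the ULN exceeds 1.89 / 1.5 = 1.26.
- Woman, 70 y, 50 kg: 0.83 mg/dL.
- Man, 70 y, 70 kg: 1.36 mg/dL.

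All three values are below the lowest assumed ceiling of 1.5.

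**Step 4. Check without Cockcroft-Gault.** By definition, daily creatinine excretion (mg) = clearance x serum creatinine x 14.4. At the ceiling with ULN 1.0, clearance is below 50 if excretion is under 50 x 1.5 x 14.4 = 1080 mg/day, and below 30 if it is under 30 x 1.5 x 14.4 = 648 mg/day. With ULN 1.3 the figures are 1404 and 842 mg/day. Both bands are reachable, 30 to <50 more easily.

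**Step 5. Dose contrast.** 300 / 200 = 1.5. Section 1.2.5 reports AUC rising linearly with dose and about 2- to 6-fold variability between patients at a given dose. It gives no human exposure by renal function.

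**The case against.** The strongest reply is that section 3.2 is itself the prompt: it makes the dose depend on clearance, and the inputs for an estimate are already to hand. Serum creatinine is needed for eligibility, weight is recorded within 7 days (section 3.6), and age and sex are known. This stands. What is missing is a recorded value and a named method, not data.

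A reader might infer that the protocol directs 300 mg in severe renal impairment. It does not; that result comes from silence. Two criteria let an investigator refuse such a patient: "No history of serious intercurrent medical illness" (2.1.1) and "Uncontrolled intercurrent illness including, but not limited to, ongoing or active infection" (2.1.2). Neither is a numeric limit, so the gap is narrowed but not closed. The creatinine ceiling also makes entry below 30 a corner case.

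A reader might also infer that clearance is nowhere defined. Section 2.1.1 names a measured 24-hour clearance, but only as the eligibility alternative. Section 3.2 does not say that it uses that value.

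Nor do the documents show harm. Their evidence of urinary elimination is from animals, and the dose contrast lies within ordinary exposure variability. QTc of 480 msec or more and potassium below 4.0 mEq/L are excluded, with limited retesting and correction allowed. ECGs are taken before and 4-8 hours after the first dose. Weekly ECG and Chem 20 then run for two cycles, past day 29, with hold-and-reduce rules for QTc. These lower the risk after dosing starts; they do not set the starting dose.

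**Conclusion.** The point holds in a limited form. Its main part is that the 200 mg start can be missed in patients at 30 to below 50 ml/min with acceptable creatinine, because no clearance is scheduled and section 3.2 names no method. The lesser part is the missing rule below 30 ml/min, which leaves the general 300 mg literally in force there.

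How many patients are affected is not known. The counts rest on an assumed formula, an assumed ULN range and profiles placed at the ceiling. With creatinine at the ULN, no profile falls below 30 and fewer fall at 30 to <50. A claim that a given share of enrolled patients would be misdosed, or that they would be harmed, goes beyond the documents, which give no age, weight or renal-function distribution. This is a safety and dosing-clarity gap worth correcting. It leaves the sample size and error rates unchanged.

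**What to change.** - In section 2.1.1 or 2.1.2, exclude creatinine clearance below 30 ml/min.
- In section 2.2.3 and the calendar, require an estimated clearance (for example Cockcroft-Gault from screening creatinine, age, sex and weight), recorded before the first dose.
- In section 3.2, state that this value sets the starting dose unless a measured 24-hour clearance is available, in which case the measured value takes precedence.
- In section 10.7, cross-refer to the renal exception in section 3.2.

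The cost is one calculated field from data already collected, with no new test, and possibly a few patients excluded or started at 200 mg. The 37-patient total and the requirement of at least 4 responses stay as they are.

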3.3 DOSING DELAYS/DOSE MODIFICATIONS

Patients will be asked to record side effects/symptoms developing or worsening on therapy on a Side Effect Diary which will be reviewed by the research nurse/PI/associate investigator during clinic visits. Treatment modifications will be made in the event of toxicities (graded based on NCI Common Toxicity Criteria for Adverse Events, version 3.0) according to the guidelines below, with dose levels as defined below:

- Dose level 0: 300mg/day
- Dose level -1: 200mg/day
- Dose level -2: 100mg/day
- Dose level -3: 100mg every other day

3.3.1 Management of Skin Toxicity

Patients will be instructed to follow a program of sun protective measures while receiving study therapy and for 3-4 weeks after discontinuing study therapy. These measures include minimizing sun-exposure, using protective clothing, hats etc., and the use of sunscreens. The aim is to reduce the risk of development of skin rash, minimize the severity of skin rash, and to minimize the requirement for dose reduction of study therapy.

If a patient develops a skin rash, The rash should be graded/assessed by a physician as soon as possible according to the CTCAE cutaneous toxicity criteria and documented accordingly

If a rash of CTCAE grade 2 or higher is detected, symptomatic treatment should be provided.

A variety of agents can be used to manage skin rashes and associated symptoms. These include mild to moderate strength steroid creams or oral corticosteroids, topical or systemic antibiotics, topical or systemic antihistamines, emollients and occasionally retinoid creams.

If a rash of CTCAE grade 3 is detected, ZD6474 should be withheld until recovery to grade 1 or below, at which point, the drug may be restarted at one dose level lower

Patients with CTCAE grade 4 rash will discontinue therapy and will not be retreated.

If grade 3 higher cutaneous toxicity recurs at reduced dose of ZD6474, the patient will permanently discontinue study treatment of ZD6474. If ZD6474 must be withheld for >3 weeks due to cutaneous toxicity, the patient will be taken off study.

3.3.2 Management of gastrointestinal (GI) toxicity

If GI toxicity is not appropriately managed this may be associated with a development of dehydration. Electrolytes should be monitored in the event of persistent vomiting or diarrhea.

3.3.2.1 Nausea and/or vomiting

In subjects who have emesis and are unable to retain study treatment, every attempt should be made to obtain control of nausea and vomiting. The dose of study treatment may be repeated if emesis occurs within 30 minutes of taking the tablets or all the tablets are seen in the emesis. Nausea, vomiting, or both may be controlled with antiemetic therapy; however, 5HT-3 antagonists are not permitted because of the potential effect on QTc interval.

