2.1.2 Exclusion Criteria

- Prior or concomitant non-von Hippel Lindau associated malignancy with the exception of adequately treated basal or squamous cell carcinoma of the skin, cervical carcinoma in situ or any other malignancy from which the patient has remained disease free for more than five years
- Known brain metastases (unless adequately resected or irradiated with no evidence of recurrence for at least 6 months)
- Patients who have had chemotherapy or radiotherapy within 4 weeks prior to entering the study or those who have not recovered from adverse events (to \leq grade 1 CTCAE v3.0) due to agents administered more than 4 weeks earlier.
- Patients may not be receiving any other investigational agents or have received treatment with a non-approved or investigational drug within 4 weeks prior to Day 1 of study treatment except those used for imaging studies. Use of 5HT-3 antagonists because of the potential effect on QTc interval
- Any concurrent medication that may cause QTc prolongation or induce Torsades de Pointes ([Appendix C](#)). Drugs listed in [Appendix C](#), Table 2, that in the investigator's opinion cannot be discontinued, are allowed however, must be monitored closely.
- Concomitant medications that are potent inducers of CYP3A4 function, such as rifampin, rifabutin, phenytoin, carbamazepine, barbiturates such as phenobarbital, or

St. John's Wort (See [Appendix D](#)).

- Clinically significant cardiac event (including symptomatic heart failure, myocardial infarction or angina) within 3 months of entry or presence of any cardiac disease that in the opinion of the Principal Investigator increases the risk of ventricular arrhythmia
- History of clinically significant arrhythmia [including multifocal premature ventricular contraction (PVC), bigeminy, trigeminy, ventricular tachycardia] that is symptomatic or requires treatment (CTCAE grade 3) or asymptomatic sustained ventricular tachycardia
- Uncontrolled atrial fibrillation. Atrial fibrillation controlled on medication is not excluded.
- Presence of Left bundle branch block
- Previous history of QTc prolongation while taking other medications that required discontinuation of that medication.
- Congenital long QT syndrome or first degree relative with unexplained sudden death under the age of 40 years

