3.3.2.2 Diarrhea

Diarrhea should be treated with standard medications to avoid dose modification or interruption, if possible. Diarrhea related to ZD6474 has been successfully managed with anti-diarrheal agents such as loperamide. Once diarrhea is determined to be related to ZD6474, an acceptable strategy for symptomatic management is initiation of loperamide 2mg po administered following the first episode, which can be repeated as frequently as every 2 hours while awake (or administered at a dose of 4mg every 4 hours during sleeping hours) (not to exceed a total of 16mg/24 hours) until the patient is diarrhea-free for 8-12 hours.

No dose modifications will be made for CTCAE grade 1 or 2 nausea, vomiting or diarrhea. If CTCAE grade 3 nausea, vomiting, or diarrhea develops despite optimal pharmacologic prophylaxis/treatment, study medication should be withheld until symptoms resolve to less than or equal to grade 1. Once the diarrhea resolves to less than or equal to grade 1, treatment with ZD6474 may recommence with a dose reduction of one level. If the toxicity reoccurs on the dose reduction pack, the subject will be withdrawn from the study. Subjects who develop grade 4 nausea, vomiting, or diarrhea will discontinue therapy with ZD6474. Subjects who are clinically unstable because of nausea, vomiting, diarrhea or other intercurrent medical illness must be admitted and evaluated using telemetry until clinically stable.

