Erythromycin	Antibiotic/GI stimulant (infection/GI motility)	F>M
Halofantrine	Anti-malarial (malaria infection)	F>M
Haloperidol	Anti-psychotic (schizophrenia, agitation)	
Ibutilide	Anti-arrhythmic (heart rhythm)	F>M
Levomethadyl	Opiate agonist (narcotic dependence)	
Mesoridazine	Anti-psychotic	

Table 1 Group 1 Drugs		
Drug (Generic Names)	Drug Class (Clinical Usage)	Comments
	(schizophrenia)	
Methadone	Opiate agonist (pain control/ narcotic dependence)	F>M
Moxifloxacin	Antibiotic / bacterial infection	
Pentamidine	Anti-infective (pneumocystis pneumonia)	F>M
Pimozide	Anti-psychotic (Tourette's tics)	F>M, TdP Cases in Literature
Probucol	Antilipemic / Hypercholesterolemia	No longer available in U.S.
Procainamide	Anti-arrhythmic (heart rhythm)	
Quinidine	Anti-arrhythmic (abnormal heart rhythm)	F>M
Sotalol	Anti-arrhythmic (heart rhythm)	F>M
Sparfloxacin	Antibiotic (bacterial infection)	
Terfenadine	Antihistamine / Allergic rhinitis	No longer available in U.S.
Thioridazine ⁸	Anti-psychotic (schizophrenia)	

Group 2. Drugs that in some reports may be associated with Torsades de Pointes but at this time lack substantial evidence of causing Torsades de Pointes

Concomitant use of these drugs is not allowed at study entry or within 2 weeks of study entry. These drugs will be allowed during the study, at the discretion of the Investigator, if considered absolutely necessary. In such cases, the patient must be closely monitored, including regular checks of QTc and electrolytes

Table 2 Group 2 Drugs		
Drug (Brand Names)	Drug Class (Clinical Usage)	Comments
Alfuzocin	Alpha 1-blocker (Benign prostatic hyperplasia)	
Amantadine	Dopaminergic/Anti-viral/Anti- infective (Parkinson's disease)	
Atazanavir	Protease inhibitor / HIV	
Azithromycin	Antibiotic (bacterial infection)	
Chloral hydrate	Sedative (sedation/insomnia)	
Clozapine	Anti-psychotic (schizophrenia)	
Dolastron	Anti-nausea (nausea and vomiting)	
Dronedarone	Anti-arrhythmic / Atrial Fibrillation	

Table 2 Group 2 Drugs		
Drug (Brand Names)	Drug Class (Clinical Usage)	Comments
Escitalopram	Anti-depressant / Major depression/ Anxiety disorders	
Famotidine	H2-receptor antagonist / Peptic ulcer/ GERD	
Felbamate	Anti-convulsant (seizures)	
Flecainide	Anti-arrhythmic (heart rhythm)	Association not clear
Foscarnet	Antiviral (HIV infection)	
Fosphenytoin	Anticonvulsant (seizures)	
Gatifloxacin	Antibiotic (bacterial infection)	
Gemifloxacin	Antibiotic (bacterial infection)	
Granisetron	Anti-nausea (nausea and vomiting)	

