Indapamide	Diuretic (stimulates urine & salt loss)	TdP Cases in Literature, QT in animals
Isradipine	Anti-hypertensive (high blood pressure)	
Lapatinib	Anti-cancer / breast cancer, metastatic	
Levofloxacin	Antibiotic (bacterial infection)	Association not clear
Lithium	Anti-mania (bipolar disorder)	
Moexipril/HCTZ	Anti-hypertensive (high blood pressure)	
Nicardipine	Anti-hypertensive (high blood pressure)	
Nilotinib	Anti-cancer / Leukemia	
Octreotide	Endocrine (acromegaly/carcinoid diarrhoea)	
Ofloxacin		
Ondansetron	Anti-emetic (nausea and vomiting)	
Oxytocin	Oxytocic / Labor stimulation	
Paliperidone	Antipsychotic, atypical / Schizophrenia	
Perflutren lipid microspheres	Imaging contrast agent / Echocardiography	
Quetiapine	Anti-psychotic (schizophrenia)	
Ranolazine	Anti-anginal / chronic angina	
Risperidone	Anti-psychotic (schizophrenia)	
Roxithromycin	Antibiotic (bacterial infection)	
Sertindole	Antipsychotic, atypical / Anxiety, Schizophrenia	
Sunitinib	Anti-cancer / RCC, GIST	
Tacrolimus	Immune suppressant	TdP Cases in Literature
Tamoxifen	Anti-cancer (breast cancer)	

Table 2 Group 2 Drugs		
Drug (Brand Names)	Drug Class (Clinical Usage)	Comments
Telithromycin	Antibiotic (bacterial infection)	
Tizanidine	Muscle relaxant	
Vardenafil	Phosphodiesterase inhibitor (vasodilator)	
Venlafaxine	Antidepressant (depression)	
Voriconazole	Anti-fungal (fungal infection)	
Ziprasidone	Anti-psychotic (schizophrenia)	

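### Section 3.3.2.1 bars 5HT-3 antagonists on study, but the Appendix C Group 2 header allows all Table 2 drugs at discretion, including three of that class

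*Combined protocol and SAP*

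**What the plan says.** Section 3.3.2.1 deals with nausea and vomiting during treatment. Antiemetics may be used, but "5HT-3 antagonists are not permitted because of the potential effect on QTc interval". No discretion clause is attached.

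Appendix C (12.3) sorts QT-related drugs into two groups. Group 1 is not allowed on study. The Group 2 header sets two rules for every drug in Table 2. Before and at entry: "Concomitant use of these drugs is not allowed at study entry or within 2 weeks of study entry". After entry: "These drugs will be allowed during the study, at the discretion of the Investigator, if considered absolutely necessary". It then requires close monitoring of any patient given such a drug, with QTc and electrolytes checked regularly. Table 2 includes dolasetron (spelled *Dolastron*), granisetron and ondansetron, each described as a drug for nausea and vomiting.

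Section 2.1.2 has two relevant pieces. Attached to the end of the bullet on investigational agents is the fragment "Use of 5HT-3 antagonists because of the potential effect on QTc interval". The next bullet excludes QT-prolonging concurrent medication, but says that Table 2 drugs which in the investigator's opinion "cannot be discontinued, are allowed however, must be monitored closely".

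Sections 3.7 and 10.9 say in general terms that the study drug should not be combined with drugs known to prolong QT. Section 3.7 points to Appendix C. Neither section names the 5HT-3 class.

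**The concern.** Two rules on the same drugs, for the same period, give different answers. The stricter one rests on QTc, which is a recognised risk of this agent. Section 1.2.5 reports QTc prolongation in 11 of 18 patients in the Japanese phase I trial and lists torsade-de-pointes among adverse events that may be related to the drug.

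The route to error is ordinary use of the protocol. A clinician treating a nauseated patient goes from 3.7 to Appendix C, looks up ondansetron by name, and finds it allowed when judged absolutely necessary. Nothing there points back to 3.3.2.1. The patient could then receive a drug that another section withholds on cardiac grounds. The site would also have a deviation to report within 7 days under 8.2.1, created by the protocol's own permission.

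**Working it through.** No sample-size, power or error-rate figure bears on this point, so the check compares the texts.

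**Step 1: does Table 2 contain drugs of the barred class?** Counting the rows across its page breaks gives 45 entries. Three are 5HT-3 antagonists: dolasetron, granisetron and ondansetron. Table 1 (Group 1) has none. The tables describe the three only by use, so placing them in the 5HT-3 class relies on standard drug classification, which the documents do not state.

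**Step 2: what does each rule say about giving one of them on study?**

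| Place | Period | Rule for these three drugs | Exception or precedence stated? |
|---|---|---|---|
| 3.3.2.1 | On study | Not permitted, because of QTc | None |
| Appendix C, Group 2 header | On study | Allowed at discretion if absolutely necessary, with close monitoring | None |
| Appendix C, Group 2 header | Entry and the 2 weeks before | Not allowed | None |
| 2.1.2, fragment | Entry | Listed among the exclusions | None |
| 2.1.2, Table 2 allowance | Entry | Table 2 drugs that cannot be stopped are allowed, closely monitored | None |
| 3.7 and 10.9 | On study | General bar on drugs known to prolong QT; 3.7 refers to Appendix C | None |

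The first two rows conflict directly: same drugs, same period, opposite answers.

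**Step 3: does another section settle it?** Sections 3.7 and 10.9 do not. If their general bar covered every drug in Appendix C, it would cancel the Group 2 allowance for all 45 entries and the grouping would have no purpose. If it covers less, the text does not say where the line falls. Section 3.7 also returns the reader to the appendix that holds the permission.

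**Step 4: what does 2.1.2 add?** Exclusion criteria are cumulative. Read as a criterion, the fragment bars a 5HT-3 user at entry whatever the next bullet allows for Table 2 drugs in general. The allowance also concerns drugs that cannot be discontinued, meaning medication already in use, and not an antiemetic started later for treatment-related nausea. So 2.1.2 is unclear drafting on this point and does not permit these drugs.

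**The case against.** The best defence is that 3.3.2.1 is the specific rule. It stands in the treatment section, covers this exact situation and gives its reason, while the Group 2 header is a generic permission over a long list. Nothing obliges an investigator to use a 5HT-3 antagonist, so avoiding the class satisfies every section. Much of this stands, and the ban is probably the intended rule. But the protocol never says so, and specificity cuts both ways: 3.3.2.1 bans by class, while Appendix C lists the drugs by name.

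A second defence is that harm is contained, and this stands too. ECGs are weekly for the first two cycles, and 3.3.3 holds the drug for QTc prolongation. Section 3.3.2 calls for electrolyte monitoring in persistent vomiting, and grade 3 nausea or vomiting leads to a hold. Patients who are clinically unstable "must be admitted and evaluated using telemetry until clinically stable". Grade 1 or 2 symptoms would also seldom make a drug absolutely necessary. These arguments lower the severity; they do not remove the contradiction.

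A reader might infer three stronger things that the documents do not support:

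- *That 2.1.2 also permits these drugs.* The fragment listed among its exclusions points the other way.
- *That the number of exposed patients can be projected from the phase I nausea and vomiting rates.* The share who would be considered for a 5HT-3 drug is not given, and those rates are not limited to the patients for whom the allowance would matter.
- *That the monthly ECG after cycle 2 measures an unmonitored gap.* A patient treated under the allowance falls under the Group 2 duty of close monitoring, so the routine interval does not describe that patient.

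**Conclusion.** The inconsistency holds for on-study use: following the Group 2 header as written can lead to a drug that 3.3.2.1 prohibits, and no stated order of precedence resolves it. It concerns 3 of the 45 Table 2 entries.

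Severity is low. No patient count, QTc effect or monitoring-gap size is claimed, because the documents give no basis for one. The Simon two-stage design, its error rates and the response endpoint are unaffected. The conclusion assumes that the three drugs belong to the 5HT-3 class, and that the 3.3.2.1 ban is the rule the sponsor means to keep.

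**What to change.** 1. In the Group 2 header of Appendix C, after the on-study allowance, add: *except 5HT-3 antagonists, which are not permitted on study (see 3.3.2.1)*.
2. Annotate the dolasetron, granisetron and ondansetron rows of Table 2 to match. Leave them in the table, since deleting them would also remove the two-week washout before entry.
3. In 2.1.2, turn the 5HT-3 fragment into a complete exclusion bullet that clearly overrides the Table 2 allowance.

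The cost is one clause, three annotations and one reformatted bullet. No visits, tests or patients are added. The only downside is losing a last-resort antiemetic, which 3.3.2.1 already denies.
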